4.4 Measure to minimize bias

For each study (*i.e.* parallel group trial and DF study) independently study participants eligible for treatment will be randomly assigned to one of the treatment arms using a computer-generated stratified block randomization code. The random allocation sequence with varying random blocks of four or eight and stratified by 2 levels of baseline infection intensity (light: <1000 EPG, and moderate plus heavy: ≥ 1000 EPG *T. trichiura* infections) will be provided by a statistician. The treatment arms will have an equal number of participants with light infection intensity, although the number of light versus moderate/heavy infections are not expected to be equal in each arm, depending on the distribution of infection intensity in the recruited cohort. The parallel group trial will be double blinded (*i.e.* study participants and the trial team/researchers conducting the treatment and assessing the outcomes will be blinded) using repacked tablets including appearance-matched placebos while the DF study will be single blinded (*i.e.* all outcome assessors except the investigators who provide the treatment and the study

Page 28 of 176

participants who get either active or placebo tablets matching in appearance will be blinded) due to the nature of this study (*i.e.* including ascending doses).

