7.1 Definition of primary endpoint

CR of co-administered ivermectin-albendazole against *T. trichiura* is the primary endpoint in our study. Since treatment success is influenced by infection intensity, stratified block randomization will be used (baseline infection intensity: light infections and moderate/heavy infections) to ensure balanced treatment groups in terms of infection intensity.

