7.3 Description of statistical methods

The primary available case analysis will include all participants with primary end point data. In addition, an intention-to-treat analysis will be conducted considering all participants with missing endpoint data as treatment failure or all as treatment success to ensure that the results are not sensitive to potential loss to follow-up bias. CRs will be calculated as the percentage of egg-positive (larvae- positive for *S. stercoralis*) participants at baseline who become egg-negative (larvae-negative) after treatment. EPG will be assessed by adding up the egg counts from the quadruplicate Kato-Katz thick smears and multiplying this number by a factor of six. For *S. stercoralis* infection no further quantification of larvae in stool will be done. The ERR of STH infection will be calculated as:

$$ERR = 1 - \frac{\frac{1}{n}e^{\sum \log(EPG_{follow} - up + 1)} - 1}{\frac{1}{n}e^{\sum \log(EPG_{baseline} + 1)} - 1}$$

In the primary model we estimate the difference among CRs by using unadjusted logistic regressions. In a subsequent analysis an adjusted logistic regression (adjustment for age, sex and weight) will be performed.

Geometric mean egg counts will be calculated for the different treatment arms before and after treatment to assess the corresponding ERRs. Bootstrap resampling method with 5,000 replicates will be used to calculate 95% confidence intervals (CIs) for ERRs and the difference between the ERRs.

Results from the stool RDT for fecal occult blood will be categorized as negative, trace and positive. For calprotectin, individuals with levels exceeding 50 μ g/g will be considered as positive and concentrations be classified into low (51–149 μ g/g), medium (150–299 μ g/g) and high (\geq 300 μ g/g) intensity [16].

Anthropometric measurements such as height and weight of school-aged children will be translated into weightfor-age, height-for-age and weight-for-height related z-scores using readily available Stata macros calculating growth indicators for children 5-19 years [37]. Body mass index and indicators for muscle and fat tissue such as MUAC and skinfold thickness will serve as additional indicators of nutritional status for adults and will further be classified using a percentiles approach to compare within populations [38].

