7.1 Definition of primary endpoint

Cure rate of co-administered ivermectin-albendazole against *T. trichiura* is the primary endpoint in our study. Since this might be influenced by infection intensity, treatment groups will be equally balanced in terms of infection intensity by 2 levels of baseline infection intensity (light infections and moderate/heavy infections).

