7.3 Description of statistical methods

The primary available case analysis will include all participants with primary end point data. In addition, an intention-to-treat analysis will be conducted considering all participants with missing endpoint data as treatment failure or all as treatment success to ensure that the results are not sensitive to potential loss to follow-up bias. CRs will be calculated as the percentage of egg-positive children at baseline who become egg-negative after treatment. EPG will be assessed by adding up the egg counts from the quadruplicate Kato-Katz thick smears and multiplying this number by a factor of six. The ERR will be calculated as:

$$ERR = 1 - \frac{\frac{1}{n}e^{\sum \log(EPG_{follow} - up + 1)}}{\frac{1}{n}e^{\sum \log(EPG_{baseline} + 1)} - 1}$$

Page 74 of 176

In the primary model we estimate the difference among CRs by using unadjusted logistic regressions. In a subsequent analysis an adjusted logistic regression (adjustment for age, sex, community, weight and height) will be performed.

Geometric mean egg counts will be calculated for the different treatment arms before and after treatment to assess the corresponding ERRs. Bootstrap resampling method with 5,000 replicates will be used to calculate 95% confidence intervals (CIs) for ERRs and the difference between the ERRs.

Results from the stool RDT for fecal occult blood will be categorized as negative, trace and positive. For calprotectin, individuals with levels exceeding 50 μ g/g will be considered as positive and concentrations be classified into low (51–149 μ g/g), medium (150–299 μ g/g) and high (\geq 300 μ g/g) intensity [19].

Anthropometric measurements such as height, weight will be translated into weight- and height-related z-scores using readily available Stata macros calculating growth indicators for children 5-19 years [33]. Body mass index and indicators for muscle and fat tissue such as MUAC and triceps skinfold thickness will serve as indicators for all ages and further be classified using a percentiles approach to compare within populations [34].

Questionnaires on physical functioning and treatment satisfaction will be evaluated by creating summary scores by summing up and transforming the single question scores according to the following formula: [(actual raw score-lowest possible raw score)/(possible raw score range)]*100 [23].

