7.3 Description of statistical methods

The primary available case analysis will include all participants with primary end point data. In addition, an intention-to-treat analysis will be conducted considering all participants with missing endpoint data as treatment failure or all as treatment success to ensure that the results are not sensitive to potential loss to follow-up bias. CRs will be calculated as the percentage of egg-positive (larvae-positive for *S. stercoralis*) children at baseline who become egg-negative (larvae-negative) after treatment. EPG will be assessed by adding up the egg counts from the quadruplicate Kato-Katz thick smears and multiplying this number by a factor of six. For *S. stercoralis* infection no further quantification of larvae in stool will be done. The ERR of STH infection will be calculated as:

$$ERR = 1 - \frac{\frac{1}{n}e^{\sum \log(EPG_{follow} - up + 1)} - 1}{\frac{1}{n}e^{\sum \log(EPG_{baseline} + 1)} - 1}$$

In the primary model we estimate the difference among CRs by using unadjusted logistic regressions. In a subsequent analysis an adjusted logistic regression (adjustment for age, sex, and weight) will be performed.

Geometric mean egg counts will be calculated for the different treatment arms before and after treatment to assess the corresponding ERRs. Bootstrap resampling method with 5,000 replicates will be used to calculate 95% confidence intervals (CIs) for ERRs and the difference between the ERRs.

Results from the stool RDT for fecal occult blood will be categorized as negative, trace and positive. For calprotectin, individuals with levels exceeding 50 μ g/g will be considered as positive and concentrations be classified into low (51–149 μ g/g), medium (150–299 μ g/g) and high (\geq 300 μ g/g) intensity [16].

Anthropometric measurements such as height and weight of school-aged children will be translated into weightand height-related z-scores using readily available Stata macros calculating growth indicators for children 5-19 years [34]. Body mass index and indicators for muscle and fat tissue such as MUAC and skinfold thickness will serve as additional indicators of nutritional status for adults and will further be classified using a percentiles approach to compare within populations [35].

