- Received no treatment, the wrong treatment or incorrect dose.
- Received an excluded concomitant therapy.

Minor protocol deviations include subjects who:

- Provided fewer stool samples than specified in the protocol
- Provided stool samples later than specified in the protocol (measurements taken outside the allowable windows given in the protocol)
- Vomiting within 1-hour post-dosing without re-treatment.

Participants with major protocol deviations will be excluded from the per-protocol population. Minor protocol deviations will remain in all analysis populations.

Page 171 of 176

Demographics and other baseline characteristics

Baseline characteristics will be calculated and presented as outlined below

	Pemb	a Island	Côte d	'Ivoire	Lao PDR		
Characteristics	ALB (n=xxx)	IVM-ALB (n=xxx)	ALB (n=xxx)	IVM- ALB (n=xxx)	ALB (n=xxx)	IVM- ALB (n=xxx)	
Age, 6-12							
Age, 13-24yrs							
Age, 25 years and above							
Sex, n (%)							
Females							
Males							
Weight, kg							
Height, cm							
T. trichiura infection							
Geometric mean EPG							
Infection intensity ^a , n (%)							
Light							
Moderate							
Heavy							
A. lumbricoides infection							
Infected, n (%)							
Geometric mean EPG							
Infection intensity ^b , n (%)							
Light							
Moderate							
Неаvy							
Hookworm infection							
Infected, no. (%)							
Geometric mean EPG							
Infection intensity ^c , n (%)							
Light							
Moderate							
Неаvy							
S. stercoralis infection ^d							
Infected, n (%)							

^a *T. trichiura* infection intensity classified according to mean eggs per gram of stool (EPG) into: light=1-999 EPG, moderate=1000-9999 EPG and heavy=≥10000 EPG

^b A. lumbricoides infection intensity classified according to mean eggs per gram of stool (EPG) into: light=1-4999 EPG, moderate=5000-49999 EPG and heavy=≥50000 EPG

^c Hookworm infection intensity classified according to mean eggs per gram of stool (EPG) into: light=1-1999 EPG, moderate=2000-3999 EPG and heavy=>4000 EPG

^d Baermann technique to detect *S. stercoralis* infection was only applied to stool samples collected in Lao PDR

Page 172 of 176

In the unadjusted analysis the differences in cure rates will be assessed using a Melded Binomial Confidence Intervals and Tests with mid-p correction as implemented in the 'exact2x2' package.

library(exact2x2)
binomMeld.test(... , # insert n[pos] and n[total]
parmtype = "difference", conf.level = 0.95, conf.int = TRUE,

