alternative = "two.sided", midp = T)

This analysis has been chosen because most biomedical journals prefer the absolute difference over the relative difference. However, adjustment for confounder or effect modifier is not possible; therefore, the adjusted analysis will use standard logistic regression.

Egg reduction rates (geometric mean based) will be calculated using the following formula

$$ERR = 1 - \frac{\frac{1}{n}e^{\sum \log(EPG_{follow} - up + 1)}}{\frac{1}{n}e^{\sum \log(EPG_{baseline} + 1)} - 1}$$

Differences in geometric mean based ERR will be analysed via bootstrap resampling using the following code

}

library(boot) difgm <- boot(data = d, statistic = diffgm, R = 2000, strata = d\$arm)

The arithmetic based ERR will be estimated in the same way.

If the sample size of study participants infected with hookworm, Ascaris lumbricoides and *Strongyloides stercoralis* is considered sufficiently large, efficacy against these parasites will be assessed in the same way. If the number of participants will be below 100 per arm the trial arms will only be compared descriptively.

Page 173 of 176

Efficacy results and estimates will be presented as outlined below

		Pemba Is	land	Côte d'Iv	oire	Lao PDR		Total		
Variab	le	ALB (n=xxx)	IVM- ALB (n=xxx)	ALB (n=xxx)	IVM- ALB (n=xxx)	ALB (n=xxx)	IVM- ALB (n=xxx)	ALB (n=xxx)	IVM- ALB (n=xxx)	
T. trich	iura									
No. of p	participants positive	for								
infectio	n Defere									
	treatment									
	After treatment									
Cure ra	te. % (95% CI)									
No. of p	participants cured n	(%)								
1	From light									
	From moderate									
	infection									
	From heavy									
Carrier	infection									
Geomet	tric mean EPG									
	Before									
	After treatment									
GMEg	g_reduction rate									
% (95%	CI)									
Arithme	etic mean EPG									
	Before									
	treatment									
	After treatment									
AM Eg	g-reduction rate,									
% (95%) A lumb	o CI) bricoid e s									
N partic	cinants positive									
T partic	Before									
	treatment									
	After treatment									
Cure ra	te, %									
N partic	cipants cured (%)									
1	From light									
	infection									
	From moderate									
	infection									
	From heavy									
Geomet	tric mean EPG									
	Before									
	treatment									
	After treatment									
Egg-red	luction rate, %									
Hookw	orm									
N partic	cipants positive	1								
	i 1			1		1		1		

Page 174 of 176

	Before					

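### Minor improvement at almost no cost: randomisation is stratified by baseline T. trichiura intensity, but neither the SAP's cure-rate comparison nor any protocol's adjusted model uses that stratum, and the handling of country in pooled subgroups is unstated

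*Combined protocol and SAP*

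**What the plan says.** - **Randomisation.** Section 4.4 of every protocol describes block randomisation "stratified by 2 levels of baseline infection intensity (light: <1000 EPG, and moderate plus heavy" at 1000 EPG or more). The SAP (Study Design) repeats the two intensity levels.
- **Reason.** Section 7.1 of the Swiss-approved, Côte d'Ivoire and Laos protocols says: "Since treatment success is influenced by infection intensity, stratified block randomization will be used". The Pemba protocol is more tentative: "Since this might be influenced by infection intensity".
- **Main comparison.** The SAP's efficacy analysis reads: "In the unadjusted analysis the differences in cure rates will be assessed using a Melded Binomial Confidence Intervals and Tests with mid-p correction". The code shown takes a count and a total per arm. The SAP explains that it prefers the absolute difference, and continues: "However, adjustment for confounder or effect modifier is not possible; therefore, the adjusted analysis will use standard logistic regression". No covariates are named.
- **Protocol models.** Section 7.3 of the Swiss-approved and Côte d'Ivoire protocols says: "In a subsequent analysis an adjusted logistic regression (adjustment for age, sex and weight) will be performed". Laos has the same list. Pemba has "adjustment for age, sex, community, weight and height". Intensity is in none of them. The SAP's Introduction says that it builds on the country protocols and will flag substantial departures.
- **Subgroups.** The SAP pools all three trials for two subgroup analyses, by age (6–12 versus 13 and over) and by intensity (light versus moderate and heavy). It does not say how country enters.
- **Already covered.** Intensity is a pre-specified subgroup. Numbers cured are tabulated by intensity class, and results are shown by country.

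**The concern.** The team thought intensity important enough to stratify on, yet no planned treatment comparison adjusts for it. When a stratification factor is prognostic, an analysis that ignores it overstates the standard error of the treatment difference. At stake is a little precision, and agreement between the analysis and the design. Separately, suppose the treatment effect differs by country and the age or intensity mix also differs by country. A pooled comparison between subgroups can then pick up the country difference and present it as an age or intensity effect.

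**Working it through.** **1. The plan's own sample size.** Section 7.2 assumes cure rates of 30% and 50%, two-sided 5% and 90% power. With unpooled variance, n = (1.960 + 1.282)² × (0.3×0.7 + 0.5×0.5) / 0.2² = 120.8, so 121 per arm. Then 121/0.85 gives 143. Both stated figures reproduce. The protocols aim for 300 per arm per country, so I use 300 × 0.85 = 255 evaluable per arm, and also 121.

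**2. Precision given up.** The documents give neither cure rates by stratum nor the share of light infections. *Assumptions:* a gap g between strata that is the same in both arms, a light share w of 50–90%, and overall rates of 30% and 50%.

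- Unstratified SE = √(0.46/n). At n = 255 this is 4.25 points.
- Stratified SE = √((0.46 − 2g²w(1−w))/n).
- Participants per arm = 255 × (1 − ratio of variances).

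| Assumed gap | Stratified SE (points) | Interval too wide by | Worth per arm |
|---|---|---|---|
| 10 points | 4.22–4.24 | 0.2–0.5% | 1–3 |
| 20 points | 4.15–4.21 | 0.8–2.2% | 4–11 |
| 40 points, equal strata | 3.86 | 10% | 44 |

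Example: at g = 0.2 and w = 0.5, √(0.46/0.44) = 1.022.

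**3. Behaviour of the planned melded mid-p interval.** All outcomes were enumerated at 255 per arm, with equal stratum sizes in both arms.

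| Assumed gap | Coverage (30% vs 50%) | Type I error (30% vs 30%) |
|---|---|---|
| None | 95.2% | 5.0% |
| 10 points | 95.2–95.3% | 4.8–4.9% |
| 20 points | 95.3–95.6% | 4.4–4.8% |
| 40 points, equal strata | 97.0% | 2.9% |

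Ignoring the strata therefore makes the procedure conservative, never liberal.

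**4. Power.** At 255 per arm it is 99.7% crude against 99.7–99.8% stratified for gaps of 10–20 points. At 121 per arm it is 90.0% against 90.2–91.3%.

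**5. What a stratified interval costs.** In 200,000 simulated trials per case, a stratum-weighted Wald interval covers 94.8–94.9% at 255 per arm. At 121 per arm it covers about 94.6–94.9%, with type I error of about 5.2–5.5%.

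**6. Country mix in pooled subgroups.** The inputs are the three studies in Figure 1 of the Laos protocol: 97/149 vs 47/149, 43/53 vs 24/55, and 53/140 vs 13/132. Their risk differences are 33.6, 37.5 and 28.0 points. *Assumptions:* these stand in for the three countries, country sizes are equal, and no country has a true subgroup effect. The artefact is the country differences weighted by subgroup share, minus the same differences weighted by the complement, over all assignments.

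| Assumed share by country | Artefact (points) | SE (points) |
|---|---|---|
| Light 60/70/80% | 0.6–1.5 | 5.1–5.2 |
| Light 50/70/90% | 1.3–3.0 | 5.1–5.2 |
| Children 40/50/60% | 0.5–1.3 | 4.7–4.8 |
| Children 20/50/80% | 1.6–3.8 | 4.7–4.8 |

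The largest is 3.8/4.75 = 0.8 SE. Over all three studies, the pooled risk difference hardly moves: 193/342 − 84/336 = 31.4 points crude, against 32.0 Mantel-Haenszel.

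**The case against.** The unadjusted primary comparison is deliberate. All four protocols name an unadjusted primary model, and the SAP gives its reason and states the limitation. Balance on intensity is secured by the randomisation, and intensity is also a subgroup factor and a row in the results tables. The precision gained is small under plausible gaps, and a near-exact method is a reasonable choice over a large-sample one. All of this stands. It is why the melded binomial should stay and why the point is minor. It does not explain why a model that is already planned as the adjusted analysis should leave out the one factor used to stratify.

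It is also fair that the omission is shown only for the protocols' models. For the SAP's own logistic model it is an inference, because the SAP lists no covariates and rests on protocols whose lists lack intensity.

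Three stronger readings are tempting, and the documents support none of them.

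- *The primary test is invalid because it ignores the strata.* Steps 2 and 3 show an unbiased estimate and error rates at or below nominal.
- *Pooled subgroup effects are confounded by country.* Each country is a separate trial, randomised within intensity strata. The arms are therefore comparable within country, and the treatment contrast inside a subgroup is not confounded by country. Only the comparison between subgroups can reflect country mix.
- *Pooling without country biases the odds ratio.* The Figure 1 counts give 3.89 crude against 4.71 Mantel-Haenszel. Much of that gap is non-collapsibility of the odds ratio, and the SAP does not say that pooled subgroups will be analysed on that scale.

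**Conclusion.** The point holds as a minor improvement at almost no cost. The stratification factor is missing from the SAP's crude comparison and from every protocol's adjusted model, and country handling in the pooled subgroups is not stated. The loss is 0.2–2.2% of interval width for gaps of 10–20 points between strata, and about 10% only in the 40-point, equal-strata case. No per-country conclusion is at risk.

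These sizes rest on assumed gaps and light shares. The country figures rest on assumed mixes and on three earlier studies, two of them from outside the trial countries, so they illustrate the mechanism rather than predict its size.

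**What to change.** - Keep the melded binomial as planned.
- In each country's adjusted logistic model, add the randomisation stratum or log baseline EPG to the covariates already planned, and report a standardised risk difference from that model. This keeps the absolute scale that the SAP prefers. A Mantel-Haenszel risk difference stratified by intensity is simpler, but it adjusts for the stratum only and not for age, sex and weight.
- For the pooled age and intensity subgroups, stratify the treatment contrast by country. If subgroups are compared with each other, include country and country-by-treatment terms.
- As a clarification, restate each country's covariate list in the SAP.

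The cost is SAP wording and a few lines of R, since all the variables are already collected. One downside should be stated in the SAP: the stratified interval is a large-sample one and can be slightly liberal, as step 5 shows, most visibly at 121 per arm.
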